Date: 15 April 2022 Page 72 of 99

Retention of study documents will be governed by the Clinical Trial Agreement.

Case Report Forms (CRF) must be completed in English. TRADENAMES® (if used) for concomitant medications may be entered in the local language. Consult the country-specific language requirements.

All written information and other material to be used by subjects and investigative staff must use vocabulary and language that are clearly understood.

Source Documents

The investigator is to maintain a list of appropriately qualified persons to whom he/she has delegated study duties. All persons authorized to make entries and/or corrections on CRFs will be included on the Amgen Delegation of Authority Form.

Source documents provide evidence for the existence of the subject and substantiate the integrity of the data collected. Source documents are filed at the investigator's site.

Source documents are original documents, data, and records from which the subject's CRF data are obtained. These include but are not limited to hospital records, clinical and office charts, laboratory and pharmacy records, diaries, microfiches, radiographs, and correspondence. Source documents may also include data captured in the IRT system (if used, such as subject ID and randomization number) and CRF entries if the CRF is the site of the original recording (ie, there is no other written or electronic record of data, such as paper questionnaires for a clinical outcome assessment or certain demographic information, such as gender, race, and ethnicity).

Data reported on the CRF or entered in the electronic CRF that are transcribed from source documents must be consistent with the source documents or the discrepancies must be explained. The investigator may need to request previous medical records or transfer records, depending on the study. Also, current medical records must be available.

The Investigator and study staff are responsible for maintaining a comprehensive and centralized filing system of all study-related (essential) documentation, suitable for inspection at any time by representatives from Amgen and/or applicable regulatory authorities.

Protocol Number: 20200195

Date: 15 April 2022 Page 73 of 99

Elements to include:

 Subject files containing completed CRFs, informed consent forms, and subject identification list

- Study files containing the protocol with all amendments, Investigator's Brochure, copies of prestudy documentation, and all correspondence to and from the IRB/IEC and Amgen
- Investigational product-related correspondence including [Proof of Receipts, Investigational Product Accountability Record(s), Return of Investigational Product for Destruction Form(s), Final Investigational Product Reconciliation Statement, as applicable
- Non-investigational product(s), and/or medical device(s) or combination product(s) documentation, as applicable

Retention of study documents will be governed by the Clinical Trial Agreement.

Remote Source Data Review and Verification

If permitted by national and/or local regulations, remote Source Data Review and Verification (rSDR/V) can be implemented. The clinical monitor should be provided with a secure, read-only access to the Electronic Medical Record (EMR) system, including all modules relevant for review. This access should be restricted to the records of only those patients who participate in the trial and who did not object to remote access to their medical records. A list of the monitors to whom remote access has been granted should be maintained. In order to prevent unauthorized access, access rights should be revoked once rSDR/V tasks have been completed for the trial. The EMR system should have an audit trail and be able to log information on who accessed data and when. Remote access to the EMR should only be possible using a two-factor authentication.

Study and Site Closure

Amgen or its designee may stop the study or study site participation in the study for medical, safety, regulatory, administrative, or other reasons consistent with applicable laws, regulations, and GCP.

Both Amgen and the Investigator reserve the right to terminate the Investigator's participation in the study according to the Clinical Trial Agreement. The investigator is to notify the IRB/IEC in writing of the study's completion or early termination and send a copy of the notification to Amgen.

Subjects may be eligible for continued treatment with Amgen investigational product(s) by a separate protocol or as provided for by the local country's regulatory mechanism. However, Amgen reserves the unilateral right, at its sole discretion, to determine

Protocol Number: 20200195

Date: 15 April 2022 Page 74 of 99

whether to supply Amgen investigational product(s) and by what mechanism, after termination of the study and before the product(s) is/are available commercially.

Compensation

Any arrangements for compensation to subjects for injury or illness that arises in the study are described in the Compensation for Injury section of the Informed Consent that is available as a separate document.

Protocol Number: 20200195

Date: 15 April 2022 Page 75 of 99

11.4 Appendix 4. Safety Events: Definitions and Procedures for Recording, Evaluating, Follow-up and Reporting

Definition of Adverse Event

Adverse Event Definition

- An adverse event is any untoward medical occurrence in a clinical study subject irrespective of a causal relationship with the study treatment.
- Note: An adverse event can therefore be any unfavorable and unintended sign (including an abnormal laboratory finding), symptom, or disease (new or exacerbated) temporally associated with the use of a treatment, combination product, medical device or procedure.
- Note: Treatment-emergent adverse events will be defined in the Statistical Analysis Plan (SAP).

Events Meeting the Adverse Event Definition

- Any abnormal laboratory test results (hematology, clinical chemistry, or urinalysis)
 or other safety assessments (eg, ECG, radiological scans, vital signs
 measurements), including those that worsen from baseline, that are considered
 clinically significant in the medical and scientific judgment of the investigator (ie,
 not related to progression of underlying disease).
- Exacerbation of a chronic or intermittent preexisting condition including either an increase in frequency and/or intensity of the condition.
- New conditions detected or diagnosed after study treatment administration even though it may have been present before the start of the study.
- Signs, symptoms, or the clinical sequelae of a suspected drug-drug interaction.
- Signs, symptoms, or the clinical sequelae of a suspected overdose of either study treatment or a concomitant medication. Overdose per se will not be reported as an adverse event/serious adverse event unless it is an intentional overdose taken with possible suicidal/self-harming intent. Such overdoses are to be reported regardless of sequelae.
- The signs, symptoms, and/or clinical sequelae resulting from lack of efficacy will be reported as adverse event or serious adverse event if they fulfill the definition of an adverse event or serious adverse event. Also, "lack of efficacy" or "failure of expected pharmacological action" also constitutes an adverse event or serious adverse event.

Events NOT Meeting the Adverse Event Definition

- Medical or surgical procedure (eg, endoscopy, appendectomy): the condition that leads to the procedure is the adverse event.
- Situations in which an untoward medical occurrence did not occur (social and/or convenience admission to a hospital).
- Anticipated day-to-day fluctuations of preexisting disease(s) or condition(s) present or detected at the start of the study that do not worsen.

Protocol Number: 20200195

Date: 15 April 2022 Page 76 of 99

Definition of Serious Adverse Event

A Serious Adverse Event is defined as any untoward medical occurrence that, meets at least 1 of the following serious criteria:

Results in death (fatal)

Immediately life-threatening

The term "life-threatening" in the definition of "serious" refers to an event in which the subject was at risk of death at the time of the event. It does not refer to an event, which hypothetically might have caused death, if it were more severe.

Requires in-patient hospitalization or prolongation of existing hospitalization

In general, hospitalization signifies that the subject has been detained (usually involving at least an overnight stay) at the hospital or emergency ward for observation and/or treatment that would not have been appropriate in the physician's office or outpatient setting. Complications that occur during hospitalization are an adverse event. If a complication prolongs hospitalization or fulfills any other serious criteria, the event is serious. When in doubt as to whether "hospitalization" occurred or was necessary, the adverse event is to be considered serious. Hospitalization for elective treatment of a preexisting condition that did not worsen from baseline is not considered an adverse event.

Results in persistent or significant disability/incapacity

The term disability means a substantial disruption of a person's ability to conduct normal life functions. This definition is not intended to include experiences of relatively minor medical significance such as uncomplicated headache, nausea, vomiting, diarrhea, influenza, and accidental trauma (eg, sprained ankle) which may interfere with or prevent everyday life functions but do not constitute a substantial disruption.

Is a congenital anomaly/birth defect

Other medically important serious event

Medical or scientific judgment is to be exercised in deciding whether serious adverse event reporting is appropriate in other situations such as important medical events that may not be immediately life-threatening or result in death or hospitalization but may jeopardize the subject or may require medical or surgical intervention to prevent 1 of

Protocol Number: 20200195

Date: 15 April 2022 Page 77 of 99

the other outcomes listed in the above definition. These events are typically to be considered serious.

Examples of such events include invasive or malignant cancers, intensive treatment in an emergency room or at home for allergic bronchospasm, blood dyscrasias or convulsions that do not result in hospitalization, or development of drug dependency or drug abuse.

Protocol Number: 20200195

Date: 15 April 2022 Page 78 of 99

Recording Adverse Events and Serious Adverse Events

Adverse Event and Serious Adverse Event Recording

- When an adverse event or serious adverse event occurs, it is the responsibility of the investigator to review all documentation (eg, hospital progress notes, laboratory, and diagnostics reports) related to the event.
- The investigator will then record all relevant adverse event/serious adverse event information in the Event Case Report Form (CRF).
- The investigator must assign the following mandatory adverse event attributes:
 - Adverse event diagnosis or syndrome(s), if known (if not known, signs or symptoms);
 - Dates of onset and resolution (if resolved);
 - Did the event start prior to first dose of investigational product
 - Assessment of seriousness;
 - Severity (or toxicity defined below);
 - Assessment of relatedness to apremilast, other protocol-required therapies and/or study-mandated activity and/or procedures;
 - Action taken; and
 - Outcome of event.
- It is not acceptable for the investigator to send photocopies of the subject's medical records to sponsor/responsible contact research organization (CRO) in lieu of completion of the Events CRF page.
- If specifically requested, the investigator may need to provide additional follow-up
 information, such as discharge summaries, medical records, or extracts from the
 medical records. In this case, all subject identifiers, with the exception of the
 subject number, will be blinded on the copies of the medical records before
 submission to Amgen.
- The investigator will attempt to establish a diagnosis of the event based on signs, symptoms, and/or other clinical information. In such cases, the diagnosis (not the individual signs/symptoms) will be documented as the adverse event/serious adverse event.

Evaluating Adverse Events and Serious Adverse Events

Assessment of Severity

The investigator will make an assessment of severity for each adverse event and serious adverse event reported during the study. The assessment of severity will be based on:

The Amgen Standard Grading Scale as show below:

Grade Definition

Protocol Number: 20200195

Date: 15 April 2022 Page 79 of 99

MILD Aware of sign or symptom, but easily tolerated

MODERATE Discomfort enough to cause interference with usual activity

SEVERE^a Incapacitating with inability to work or do usual activity

a An event is defined as 'serious' when it meets at least 1 of the predefined outcomes as described in the definition of a serious adverse event, NOT when it is rated as severe.

Assessment of Causality

- The investigator is obligated to assess the relationship between investigational product(s) protocol-required therapies, and/or study-mandated activity and/or procedure(s) and each occurrence of each adverse event/serious adverse event.
- Relatedness means that there are facts or reasons to support a relationship between investigational product and the event.
- The investigator will use clinical judgment to determine the relationship.
- Alternative causes, such as underlying disease(s), concomitant therapy, and other
 risk factors, as well as the temporal relationship of the event to study treatment
 administration will be considered and investigated.
- The investigator will also consult the Investigator's Brochure and/or Product Information, for marketed products, in **their** assessment.
- For each adverse event/serious adverse event, the investigator must document in the medical notes that he/she has reviewed the adverse event/serious adverse event and has provided an assessment of causality.
- There may be situations in which a serious adverse event has occurred and the
 investigator has minimal information to include in the initial report. However, it is
 very important that the investigator always make an assessment of causality for
 every event before the initial transmission of the serious adverse event data.
- The investigator may change **their** opinion of causality in light of follow-up information and send a serious adverse event follow-up report with the updated causality assessment.
- The causality assessment is 1 of the criteria used when determining regulatory reporting requirements.

Protocol Number: 20200195

Date: 15 April 2022 Page 80 of 99

Follow-up of Adverse Event and Serious Adverse Event

The investigator is obligated to perform or arrange for the conduct of supplemental
measurements and/or evaluations as medically indicated or as requested by
Amgen to elucidate the nature and/or causality of the adverse event or serious
adverse event as fully as possible. This may include additional laboratory tests or
investigations, histopathological examinations, or consultation with other health
care professionals.

- If a subject is permanently withdrawn from protocol-required therapies because of a serious adverse event, this information must be submitted to Amgen.
- If a subject dies during participation in the study or during a recognized follow-up period, the investigator will provide [Amgen] with a copy of any postmortem findings including histopathology.
- New or updated information will be recorded in the originally completed Events CRF.
- The investigator will submit any updated serious adverse event data to Amgen within 24 hours of receipt of the information.

Reporting of Serious Adverse Event

Serious Adverse Event Reporting via Electronic Data Collection Tool

- The primary mechanism for reporting serious adverse event will be the electronic data capture (EDC) system.
- If the EDC system is unavailable for more than 24 hours, then the site will report the information to Amgen using a paper-based Serious Adverse Event Contingency Report Form (also referred to as the electronic Serious Adverse Event (eSAE) Contingency Report Form) (see Figure 11-1) within 24 hours of the investigator's awareness of the event.
- The site will enter the serious adverse event data into the electronic system as soon as it becomes available.
- After the study is completed at a given site, the EDC system will be taken off-line to prevent the entry of new data or changes to existing data.
- If a site receives a report of a new serious adverse event from a study subject or receives updated data on a previously reported serious adverse event after the EDC system has been taken off-line, then the site can report this information on the paper-based Serious Adverse Event Contingency Report Form (see Figure 11-1).
- Once the study has ended, serious adverse event(s) should be reported to Amgen (regardless of causality) if the investigator becomes aware of a serious adverse event. The investigator should use the paper-based Serious Adverse Event Contingency Report Form to report the event.

Protocol Number: 20200195

Date: 15 April 2022 Page 81 of 99

Figure 11-1. Sample Electronic Serious Adverse Event Contingency Form

A	Ele	ectron	ic Se	erio	us Ad	vers	e E	ver	nt	Coi	ntin	nge	nc	y	Re	po	ort Fo	rm
Study # 20200195 AMG 407						For I	Rest	Restricted Use										
Allio Tol																		
Reason for reporting thi	is even	t via fax																
The Clinical Trial Databa	ase (eg	. Rave):																
☐ Is not available due to	interne	t outage	at my s	ite														
☐ Is not yet available for	this stu	dv																
☐ Has been closed for th		-																
< <for cor<="" td="">npletio	n by CO	M prio	r to	providing	g to si	tes:	SELI	ECT	ror	TYF	PE II	V A	FA	X#>	*			</for>	npletio	n by CO	M prio	r to	providing	g to si	tes:	SELI	ECT	ror	TYF	PE II	V A	FA	X #>	*		
1. SITE INFORMATION													_					
Site Number		Inv	estigator										Coun	Iry				
Reports	er			Phon	e Number						Fax	Numbe	er					
				()						()					
2. SUBJECT INFORMATIO	N																	
Subject ID Number		Age at eve	nt onset				Sex	x		Ra	эсе				cable,	prov	vide End of 5	itudy
	Τ-Τ							JF D	ЭΜ				da	ite				
If this is a follow-up to an event	reported	in the EDC	system	(eg, l	Rave), prov	ide the	advers	e eve	nt te	rm:								
and start date: Day Month	٠  	Year	_															_
3. SERIOUS ADVERSE EVI	ENT																	
Provide the date the Investigator			iis inforn	nation	: Day	Month	Ye	ear	_									
Serious Adverse Event diagnosis or If diagnosis is unknown, enter signs						Check only if	C:	freerio		Is there			onehip				Dutoome of Event	Check only Fevent is
and provide diagnosis, when known,		V-				event	8	Senio	us I		may h	ave be	en cau	sed b	197			related to study
up report		Date 8	tarted	Da	ite Ended	occurred before	event serious?	Critical	nia	IP or en	Amgen	device		to edi	niniste	r the	Not resolved -Fatal	procedure
List one event per line. If event is fata cause of eeath. Entry of "death" is not						first dose	i i	(386									-unu -Unknown	eg, blape;
as this is an outcome.	acceptance				Marie Wass	of IP	8	code	a -	<ptterio< td="">-1	device-		evice>	_	tevios	4		</ptterio<>	-1	device-		evice>	_	tevios	4	
		Day Mon	ui rear	uay	Month Year	1	-	belov		b/ Yes		1 Yes						
							□Yea		Т	\top	\top							
							□No	₩	+	+	_	\vdash			Ш	 	—	
							□Yea □No											
		+		\vdash			□Yea	\vdash	+	+	+	Н	Н	\vdash	Н	\vdash	+	\vdash
							□No											
Serious 01 Fatal Criteria: 02 Immediately life-thr	natenina				ged hospitali: nificant disab		nacitu										th defect nt serious ev	oned.
								-42.5	This.	EV								
4. Was subject hospitalize			alizatio	n pr	viongea a	iue this	ever	nt? L	1140						mpie	se a	III OT Sectio	n s
Day	ate Admit Month	tted Year								Day	Date D)iach: Ionth		d Yea				
Jay	Jilal	1-Call			$\overline{}$					Jay	"	- Section 1		, cd	_			
5. Was IP/drug under study	, admin	istorodita	kon ne	ior to	this over	#2 FN		(ac If-	wee	nless	0.000	nolote	, all c	of C	ontic	n 5		
o. Was it rurug under Study	y autiliti	nstereu/la	wen hu	.51 10	uns ever	Prior to					2 5011	prese	_		Take	_		
	-	Date of Ini	tial Dose		Date of D			188	Ro		Frequ	jency	wi	ith Pr	roduc	t		
							-1					-			being		Lot#and	Corial #
															tered nanen	đν	LOC# and	Selial #
													disc	contin	nued	7		
IP/Amgen Device:		Day Mont	h Yea	r Da	y Month	Year	-	\rightarrow		\rightarrow			03	With	held	+		
																	Lot# Unknown	
																	Serial #	
< <ip device="">></ip>	pon labol			- [Unevellebi Unknown	e/
				$\neg \vdash$			\top	$\neg \uparrow$		$\neg \uparrow$			Т			\top	Lot#	
																	Unknown Serial #	
																	octrai #	
< <ip device="">></ip>	non labor																Unevellebi	le /

FORM-056006

Version 7.0 Effective Date: 1 February 2016
Page ∥ of 3

Protocol Number: 20200195

Date: 15 April 2022 Page 82 of 99

A	Electronic Serious Adverse Event Contingency Report Form
Study # 20200195 AMG 407	For Restricted Use

			a	Site Nu	umber				Su	ubject II) Num	ber						
								\bot										
6. CONC	OMITANT N	/IEDICATI	ONS (eg, ch	emot	hera	py) Ar	y Me	dication	ns? 🗆 1	No 🗆	Yes If y	es, pl	lease con	nplete:			
Medication Name(s)			Start Date			Stop Date C		Co-8	uspect Con		tinuing Yæ√		0088	Route		Treatn No.	nent Med Yee	
						 			140-	100*	160-	100*	\vdash			 	140*	100-
						_				 						—		
						Т							Г					
						\vdash							\vdash					
7 RFLF	VANT MED	ICAL HIST	TORY	linclu	de da	tes .	allerni	es ar	nd anı	v relev	ant n	rior th	eran	vi				
				,														
8. RELE	VANT LAB	ORATORY	/ VAL	UES (i	includ	le ba	seline	valu	es) A	ny Rele	vant l	aborate	ory va	lues? 🗆	No □ Yes	If yes, pk	ease con	nplete:
	Test																	
Date	Unit												\neg					
Day V	lonth Year							\top		1								
9. OTHE	R RELEVA	NT TESTS	diag	nosti	cs an	d pro	cedur	es)		Any C	ther F	Relevan	t tests	? 🗆 N	o 🗆 Yes	lf yes, pk	ease con	nplete:
	Date Ionth Year			Addi	tional	Test	5			-			Resi	ults			Units	,

FORM-056006

Protocol Number: 20200195

Date: 15 April 2022 Page 83 of 99

A C4d., # 2020040E	Electronic Serious Adverse Event Contingency Report Form
Study # 20200195 AMG 407	For Restricted Use

	Site Number			8	Bubjeo	at ID N	lumbe	90		- 6		
 CASE DESCRIPTION (Provide event in section 3, where relationsh 					d in a	sectio	on 3)	Provide	add	itions	l pages if ne	cessary. For each
event in Section 6, where relationship	p res, pieuse p	10010	_ 1000	oriale.								
Signature of Investigator or Designee -						Title						Date
I confirm by signing this report that the info causality assessments, is being provided to a Qualified Medical Person authorized by the	Amgen by the invest	igator j	for this									

Page 3 of 3

Protocol Number: 20200195

Date: 15 April 2022 Page 84 of 99

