7.1 Discontinuation of Study Treatment

Subjects (or a legally authorized representative) can decline to continue receiving investigational product and/or other protocol-required therapies and/or procedures at any time during the study but continue participation in the study. If this occurs, the investigator is to discuss with the subject the appropriate processes for discontinuation from investigational product or other protocol-required therapies and must discuss with the subject the possibilities for continuation of the Schedule of Activities (see Table 1-1) including different options of follow-up (eg, in person, by phone/mail, through family/friends, in correspondence/communication with other treating physicians, from the review of medical records) and collection of data, including endpoints, adverse events, and must document this decision in the subject's medical records. Subjects who have discontinued investigational product and/or other protocol-required therapies and/or procedures should not be automatically removed from the study. Whenever safe and feasible, it is imperative that subjects remain on-study to ensure safety surveillance and/or collection of outcome data.

Reasons for early removal from protocol-required investigational product(s) or procedural assessments may include any of the following:

- decision by Sponsor
- lost to follow-up
- death
- adverse event
- subject request
- lack of efficacy
- protocol deviation
- pregnancy

Protocol Number: 20200195

Date: 15 April 2022 Page 41 of 99

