9.2 Sample Size Determination

The primary endpoint is the achievement of PPPASI-50 response at week 16. The sample size estimation is based on the results of the phase 2 (CC-10004-PPP-001 [20200055]) study. Assuming a proportion of subjects achieving PPPASI-50 response at week 16 of 40% and 65% for the placebo group and the apremilast 30 mg BID group,

Protocol Number: 20200195

Date: 15 April 2022 Page 52 of 99

respectively, a sample size of approximately 170 subjects in total (85 subjects per group) provides 90% power using a chi-square test with a 2-sided alpha of 0.05. A dropout rate of 5% during double-blind placebo-controlled treatment period is anticipated.

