5.1 Safety Related Definitions

5.1.1 Treatment-emergent Adverse Events (TEAEs)

Any AEs that begin or worsen on or after the first dose of IP through 30 days after the last dose of IP or study treatment discontinuation date, whichever is later.

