9.6.2 Adverse Events

Adverse events will be analyzed in terms of treatment-emergent adverse events (TEAEs) defined as any AEs that begin or worsen on or after the first dose of IP through 30 days after the last dose of IP or study treatment discontinuation date, whichever is later. The Medical Dictionary for Regulatory Activities (MedDRA) version 24.0 or higher will be used to code all events categorized as adverse events to a system organ class and a preferred term.

An **overview** of the following AE categories will be provided.

AE Categories:

- TEAE
- Drug-related TEAE
- Severe TEAE
- Serious TEAE
- Serious Drug-related TEAE
- TEAE Leading to Drug Interruption
- TEAE Leading to Drug Withdrawal
- TEAE Leading to Death

Summary of the above AE categories for the subgroups in Section 4.2 will be provided.

Tables summarizing the incidence of TEAEs by SOC and/or PT will be generated for each of the followings:

- All TEAEs
- Drug-related TEAE
- TEAEs by maximum severity
- Serious TEAE
- Serious Drug-related TEAE
- TEAE Leading to Drug Interruption
- TEAE Leading to Drug Withdrawal
- TEAE Leading to Death
- First onset and new event of TEAE by exposure interval
 - Placebo controlled period (weeks): ≤ 1, > 1 to ≤ 2, > 2 to ≤ 4, > 4 to ≤ 8, > 8 to ≤ 12, > 12 to ≤ 16, > 16
 - Apremilast-exposure period (weeks): ≤ 1, > 1 to ≤ 2, > 2 to ≤ 4, > 4 to ≤ 8, > 8 to
 ≤ 12, > 12 to ≤ 16, > 16 to ≤ 28, > 28 to ≤ 40, > 40 to ≤ 52, > 52
- TEAE for the subgroups in Section 4.2

Tables summarizing the incidence of TEAEs by PT will be generated for each of the followings:

- TEAEs by NSAIDs status
- Most frequent TEAEs (subject incidence ≥ 5% in any group or another cut-off if justified)
- Most frequent TEAEs by maximum severity (subject incidence ≥ 5% in any group or another cut-off if justified)
- Most frequent TEAE for the subgroups in Section 4.2 (subject incidence ≥ 5% in any group or another cut-off if justified)
- First onset of most frequent TEAE by exposure interval (subject incidence ≥ 5% in any group or another cut-off if justified)
 - Placebo controlled period (weeks): ≤ 1, > 1 to ≤ 2, > 2 to ≤ 4, > 4 to ≤ 8, > 8 to ≤ 12, > 12 to ≤ 16, > 16
 - Apremilast-exposure period (weeks): ≤ 1, > 1 to ≤ 2, > 2 to ≤ 4, > 4 to ≤ 8, > 8 to
 ≤ 12, > 12 to ≤ 16, > 16 to ≤ 28, > 28 to ≤ 40, > 40 to ≤ 52, > 52

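### Appendix 4 makes lack of efficacy itself an adverse event and the SAP does not separate it, so the week 0-16 aggregate TEAE rows may understate apremilast's excess over placebo

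*Protocol*

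**What the plan says.** Protocol Section 11.4 (Appendix 4), in the list of events that meet the adverse event definition, deals with lack of efficacy in two consecutive sentences. The first begins "The signs, symptoms, and/or clinical sequelae resulting from lack of efficacy will be reported as adverse event" and applies only where those signs or symptoms satisfy the AE or SAE definition. The second carries no such condition: "Also, 'lack of efficacy' or 'failure of expected pharmacological action' also constitutes an adverse event or serious adverse event". In the companion list of events that are not adverse events, the entry on pre-existing disease reads "Anticipated day-to-day fluctuations of preexisting disease(s) or condition(s) present or detected at the start of the study that do not worsen".

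Protocol Section 8.4.4.1.1 makes the investigator responsible for reporting every adverse event after the first dose. Appendix 4 leaves the definition of treatment-emergent to the SAP. SAP 5.1.1 defines it by timing: "Any AEs that begin or worsen on or after the first dose of IP through 30 days after the last dose of IP", or the treatment discontinuation date if later. SAP 9.6.2 gives an overview (any, drug-related, severe and serious TEAE, TEAE leading to interruption, withdrawal or death) and adds: "Tables summarizing the incidence of TEAEs by SOC and/or PT will be generated for each of the followings". None of these tables excludes lack of efficacy or shows it separately.

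Protocol Section 7.1 introduces its list of stop reasons with "Reasons for early removal from protocol-required investigational product(s) or procedural assessments may include any of the following". Adverse event and lack of efficacy are separate entries, and no rule covers a case that is both.

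**The concern.** In a placebo-controlled efficacy trial, lack of efficacy is the efficacy outcome. If it is also recorded as an adverse event, part of the efficacy difference enters the safety comparison with the opposite sign: the less effective arm collects more events. TEAEs compared with placebo are a stated secondary endpoint (Protocol Section 3, SAP 2.1). SAP 9.6.1 plans no inferential testing, so readers will take the descriptive aggregate rows at face value.

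The two Appendix 4 sentences also give roughly 45 sites (Protocol 4.1) room to record the same situation differently. How often lack of efficacy is entered as an event is then neither known nor controlled.

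**Working it through.** **Planning rates.** Protocol 9.2 has "Assuming a proportion of subjects achieving PPPASI-50 response at week 16 of 40% and 65% for the placebo group" and the apremilast group, respectively. With 85 per group, the pooled mean rate is 0.525 and

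z = [0.25 × √85 − 1.96 × √(2 × 0.525 × 0.475)] / √(0.40 × 0.60 + 0.65 × 0.35) = (2.305 − 1.384) / 0.684 = 1.35,

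which gives 91.1% power. The stated 90% reproduces, and nothing here changes it. Planned non-response is q = 1 − 0.40 = 0.60 on placebo and 1 − 0.65 = 0.35 on apremilast.

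**Any TEAE.** Three inputs are assumptions, because the documents do not give them:

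- t, the rate of other TEAEs: 0.50 on placebo, 0.65 on apremilast
- f, the share of non-responders with lack of efficacy recorded as an AE, equal in both arms
- independence of the two kinds of event

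Observed rate = 1 − (1 − t)(1 − f × q).

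| f | Placebo | Apremilast | Excess (points) |
|---|---|---|---|
| 0 | 50.0% | 65.0% | 15.0 |
| 10% | 1 − 0.50 × 0.940 = 53.0% | 1 − 0.35 × 0.965 = 66.2% | 13.2 |
| 25% | 1 − 0.50 × 0.850 = 57.5% | 1 − 0.35 × 0.9125 = 68.1% | 10.6 |
| 50% | 1 − 0.50 × 0.700 = 65.0% | 1 − 0.35 × 0.825 = 71.1% | 6.1 |

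**Other assumed values of t, same formula.**

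| Other TEAEs, placebo vs apremilast | f = 0 | f = 10% | f = 25% | f = 50% |
|---|---|---|---|---|
| 50% vs 70% | 20.0 | 18.0 | 15.1 | 10.2 |
| 40% vs 60% | 20.0 | 17.8 | 14.5 | 9.0 |
| 40% vs 50% | 10.0 | 8.2 | 5.4 | 0.7 |

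**Direction.** In the 50% vs 65% case the placebo rate rises by f × 0.60 × 0.50 = 0.300f and the apremilast rate by f × 0.35 × 0.35 = 0.1225f. The excess shrinks unless f on apremilast is more than 0.300 / 0.1225 = 2.4 times f on placebo.

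**TEAE leading to withdrawal.** Anticipated double-blind dropout is 5% for all reasons, or 0.05 × 85 = 4.25 subjects per arm. Suppose other TEAEs lead to withdrawal in 2% vs 6%, an excess of 4 points.

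- If lack-of-efficacy stops of 2% vs 0.5% are also entered as AEs, the row reads 4% vs 6.5%, an excess of 2.5 points.
- If they are 4% vs 1%, it reads 6% vs 7%, an excess of 1 point.

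All these withdrawal rates are assumed. Their totals lie at or slightly above the planned 5%, but Protocol 7.1 lets a subject stop treatment and stay in the study, so the two quantities need not match.

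**The case against.** The strongest reply is that the 40% and 65% are PPPASI-50 response rates, not rates of recorded events. A subject who improves by 45% is a non-responder, and nothing in the documents turns a missed PPPASI-50 into an AE. An investigator has to enter it, and fluctuation without worsening is excluded. The value of f may be small, and at f = 10% the 15-point gap moves by under 2 points. This stands: the effect depends on recording practice.

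A reader might go further and infer that apremilast's tolerability cost is hidden. The documents do not support that. SAP 9.6.2 tabulates by preferred term, by severity and by exposure interval, and summarises events of interest. Diarrhea, nausea and headache, listed in Protocol 2.3 among the common events, stay visible by arm. An event recorded as lack of efficacy would appear under its own term.

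A reader might also infer that every lack-of-efficacy stop becomes a TEAE leading to withdrawal, or that the drug-related rows are distorted in the same way. The first needs a separate AE entry with that action taken, and SAP 9.2 tabulates the reasons for ending treatment, which gives a partial check. The second needs a causal judgement (SAP 5.1.2, Appendix 4). A serious event must still meet a seriousness criterion.

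Finally, the table shells are not among the documents and could contain an exclusion. SAP 9.6.2 refers to them for several definitions of events of interest, but not for this.

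What survives is that the unconditional sentence is current text, all AEs must be reported, and the SAP has no separate handling.

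**Conclusion.** The point holds for the week 0-16 aggregate rows: any TEAE, severe TEAE, and TEAE leading to interruption or withdrawal. To the extent that lack of efficacy is recorded as an AE, and unless it is recorded far more readily on apremilast, those rows understate apremilast's excess. The direction follows from planned non-response of 60% vs 35%.

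The size cannot be fixed from the documents. Under the assumptions shown it runs from about 2 points of a 15-point excess at f = 10% to about 9 points at f = 50%. The withdrawal row is the most fragile, because a few subjects can change it. The planning rates alone do not show that the comparison is biased; they show which way it would lean.

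The primary estimand is untouched, since stopping for lack of efficacy and stopping for an adverse event both count as non-response. In the apremilast-exposure period there is no concurrent placebo comparison to distort.

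**What to change.** Before the week 16 database lock, add to SAP 9.6.2 a prespecified list of lack-of-effect preferred terms. Keep all recorded AEs in the main tables, and present the TEAE overview and the TEAE-leading-to-withdrawal rows both with and without the listed terms. Confine the list to lack of effect: Appendix 4 separately counts exacerbation of a pre-existing condition as an adverse event.

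Reconcile the two Appendix 4 sentences with each other and with the separate stop reasons in Protocol 7.1, including how a case that fits both reasons is recorded. Which reporting rule applies is for the sponsor to decide.

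The SAP change costs one term list and a few extra table rows, and no data are lost. Any change to the Appendix 4 wording would need a protocol amendment, but the with-and-without display does not depend on it.
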